## LIST OF ABBREVIATIONS AND DEFINITION OF TERMS

The following abbreviations and special terms are used in this study Clinical Study Protocol.

---

Abbreviation or special term	Explanation
ALT	alanine transferase
BhCG	beta human chorionic gonadotrophin
bid	twice daily
BMI	body mass index
CDA	Canadian Diabetes Association
Cr	creatinine
ECG	electrocardiogram
eGFR	estimated glomerular filtration rate
FPG	fasting plasma glucose
MDRD	The Modification of Diet in Renal Disease equation to estimate GFR
OD	once daily
pc	postcibum (postprandial)
PHRI	Population Health Research Institute
po	taken orally
RCT	randomized controlled trial
SAE	serious adverse event
sc	taken subcutaneously
SGLT2	sodium glucose co-transporter 2
SMBG	self-monitoring of capillary blood glucose
T2DM	type 2 diabetes mellitus

---

## 1. INTRODUCTION

### 1.1 Background and rationale

The current approach to treating type 2 diabetes mellitus (T2DM) is to add progressively higher doses and numbers of glucose-lowering drugs to lifestyle approaches. People with type 2 diabetes are therefore taking such drugs from shortly after diagnosis until the end of their lives. A different, novel approach that intensively treats patients with several agents and lifestyle approaches for up to 2-4 months, followed by cessation of all drugs, may achieve a drug-free metabolic remission that could last for months to years. Such an approach has not been formally tested. However, a) evidence from small studies suggesting that approximately 40% of newly diagnosed patients can achieve a remission with short-term intensive treatment with insulin; b) a growing list of glucose-lowering drugs with novel mechanisms of action; and c) the appeal of remission-induction versus lifelong chronic therapy highlights the need to characterize strategies for metabolic remission of diabetes and to identify the optimal therapies and regimens for achieving remission.

We have just completed a peer-reviewed pilot trial of this approach at our centre. Eighty three people with T2DM diagnosed within the prior 3 years were randomized to 3 treatment groups: a) an 8-week intensive metabolic intervention; b) a 16-week intensive metabolic intervention; and c) standard diabetes therapy. The intensive metabolic intervention combined lifestyle therapy and basal insulin glargine, metformin and acarbose and aimed at achieving normoglycemia on therapy. We found that an 8-16-week course of therapy was safe and feasible and induced remission in up to 40% of people with early T2DM. These data illustrate that metabolic interventions such as the one proposed herein can be successfully implemented and have the potential to induce diabetes remission not requiring glucose-lowering therapies. The proposed multicentre randomized controlled trial will assess the remission-related efficacy of a sodium glucose co-transporter 2 (SGLT2) inhibitor-based regimen in a broader set of patients.

### 1.2 Hypothesis and research questions

#### **Hypothesis:**

In patients with early type 2 diabetes, a short-term intensive metabolic intervention comprising dapagliflozin (Forxiga), metformin, basal insulin glargine and lifestyle approaches will be superior to standard diabetes therapy in achieving sustained diabetes remission.

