#### **Primary research question:**

In patients with recently-diagnosed T2DM, does a 12-week course of Forxiga, metformin, basal insulin glargine and lifestyle approaches achieve drug-free diabetes remission in a higher proportion of patients than standard diabetes therapy at 24 weeks after randomization? Diabetes remission is defined as a HbA1C < 6.5% off glucose-lowering agents for at least 12 weeks.

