**Secondary research questions:**

- 1) Compared to the control group, does this therapeutic approach achieve drug-free diabetes remission in a higher proportion of patients than standard diabetes therapy at 36, 48 and 64 weeks after randomization?
- 2) Compared to the control group, does this therapeutic approach achieve drug-free HbA1C <6.0% in a higher proportion of patients than standard diabetes therapy at 24, 36, 48 and 64 weeks after randomization?
- 3) Compared to the control group, does this therapeutic approach achieve drug-free diabetes regression in a higher proportion of patients than standard diabetes therapy at 24, 36, 48 and 64 weeks after randomization? Diabetes regression is defined as HbA1C 6.5-6.9% off glucose-lowering agents for at least 12 weeks.
- 4) What HbA1C levels are achieved in the intervention group and the control group at 12, 24, 36, 48 and 64 weeks after randomization?
- 5) What rates of hypoglycemia are observed in the intervention group and the control group during 64 weeks of follow-up?
- 6) What is the change in weight, body mass index (BMI), waist circumference and waist/hip ratio from baseline to 12, 24, 36, 48 and 64 weeks in the intervention group and the control group?
- 7) Are age, gender, ethnicity, diabetes duration, smoking, family history of diabetes, baseline BMI, waist circumference, HbA1C or fasting plasma glucose (FPG) determinants of diabetes remission at 24 weeks after randomization?

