#### **5.3.3 Monitoring for hyperglycemia relapse during the maintenance phase of the trial**

In all participants, HbA1C will be drawn during week 12 of the trial. At the end of week 12, glucose-lowering medications will be discontinued in all participants with a HbA1C <7.3%, and insulin will be tapered over a 5-day period. Participants will be encouraged to continue with lifestyle modifications and regular home glucose monitoring (i.e. at least 5 fasting capillary measures per week). They will meet with research staff every 2-4 months during the maintenance phase of the trial to review any challenges in achieving and maintaining exercise and weight loss goals. Participants will be assessed by research staff every 1-2 months by telephone to review adherence to lifestyle therapy, SMBG readings and to screen for symptoms of hyperglycemia.

It is possible that glucose levels may quickly rise after glucose-lowering drugs are stopped in some of the participants whose HbA1C is <7.3% on these drugs. This rise may not be detected with HbA1C levels due to the well-known time-lag between rising glucose levels and rising HbA1C levels.

In light of the above, hyperglycemia relapse will be defined as follows:

- a. a HbA1C  $\geq$  7.0% at 24, 36, 48 and 64 weeks; or
- b. reinitiation of glucose-lowering drugs; or

- c. capillary glucose values  $\geq 10$  mmol/L on  $\geq 50\%$  of SMBG readings over 1 week in the absence of an acute illness.

All participants identified to have hyperglycemia relapse will receive standard glycemic management according to the judgment of their physician or investigator. Participants found to have HbA1C  $\geq 7.3\%$  on therapy during week 12 of the trial will also receive standard glycemic management. These participants will continue to be contacted by telephone every 1-2 months to review SMBG readings, medication adherence and side effects.

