### **6.2 Study outcomes**

#### **6.2.1 Primary and secondary outcomes**

The primary outcome is drug-free diabetes remission, defined as a HbA1C < 6.5% without use of glucose-lowering agents for at least 12 weeks. Related outcomes to be analyzed include complete diabetes remission, defined as a HbA1C < 6.0% without use of glucose-lowering agents for at least 12 weeks, and diabetes regression, defined as a HbA1C of 6.5-6.9% without use of glucose-lowering agents for at least 12 weeks.

HbA1C will be measured in the local labs at 12, 24, 36, 48 and 64 weeks after randomization, during which use of glucose-lowering medications will also be ascertained. FPG will also be measured in the local lab at 16 weeks. All FPG levels will be measured approximately 48 hours after the last dose of any glucose-lowering medication unless fasting capillary glucose rises above 12 mmol/L.

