### **11.2 Statistical analyses**

All group comparisons will be conducted according to the intention-to-treat principle with inclusion of data from all participants according to their treatment group assignment, regardless of adherence to therapy. The primary outcome in this study is the proportion of patients in the intervention group who achieve drug-free diabetes remission 24 weeks after randomization compared to the control group. The treatment groups will be compared using a chi-squared test with  $\alpha = 0.05$  level of significance. The outcome will be reported as a risk difference in the induction of remission between the intervention group and the control group with 95% confidence interval. Any individual who withdraws/drops out prior to the 24, 36, 48 and 64 week visit will be classified as not having achieved drug-free diabetes remission at that point in time. Participants who fail to achieve remission or have hyperglycemia relapse will be censored with respect to diabetes remission outcomes.

For secondary analyses, a chi-squared test will be used for dichotomous outcomes and a two-sample t-test (or a non-parametric equivalent) for continuous outcomes. Secondary outcomes will be used only for generation of new hypotheses. Clinical and metabolic predictors of the successful induction of diabetes remission will be evaluated using logistic regression modeling. We do not plan to perform any interim analyses in this trial.

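### The hypothesis is about sustained remission, but no planned outcome measures it, and the censoring sentence that might supply one is undefined for a comparison of proportions

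*Combined protocol and SAP*

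**What the plan says.** Section 1.2 hypothesises that the intervention "will be superior to standard diabetes therapy in achieving sustained diabetes remission". The word sustained is not defined there or later. Section 1.1 motivates the trial by a drug-free remission that might persist for months or years.

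Section 6.2.1 gives the outcome: "The primary outcome is drug-free diabetes remission, defined as a HbA1C < 6.5% without use of glucose-lowering agents for at least 12 weeks". Under Section 11.2 the primary comparison is the proportion of intervention patients "who achieve drug-free diabetes remission 24 weeks after randomization compared to the control group", tested by chi-squared and reported as a risk difference. The first secondary question asks whether the approach will "achieve drug-free diabetes remission in a higher proportion of patients than standard diabetes therapy at 36, 48 and 64 weeks after randomization". These later comparisons are also chi-squared tests, and Section 11.2 declares secondary outcomes hypothesis-generating only. No outcome covers all visits together, and no analysis of duration of remission or time to relapse is planned.

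Three further rules bear on the point:

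- Section 11.2 analyses all participants as randomized, and counts anyone who withdraws before a visit as not in remission at that visit.
- Section 11.2 then adds: "Participants who fail to achieve remission or have hyperglycemia relapse will be censored with respect to diabetes remission outcomes".
- Section 5.3.3 defines relapse by any of three criteria: a HbA1C at or above "7.0% at 24, 36, 48 and 64 weeks; or", then "reinitiation of glucose-lowering drugs; or", then a week of high home glucose readings. Drug-free HbA1C of 6.5-6.9% is a separate state, regression, and does not by itself meet the HbA1C criterion for relapse.

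**The concern.** The hypothesis and rationale concern durability, while the only confirmatory test is at week 24, about 12 weeks after drugs are stopped. Later proportions can describe durability only if the plan says how a person's earlier visits affect the later ones. The censoring sentence is the one place that might do so, and it can be read in ways that give different numerators and denominators.

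Two things are at stake. A positive week-24 result could be reported as confirming a hypothesis of sustained remission that it does not test. The week 36, 48 and 64 results could also differ with how the analyst reads one word, and a choice made after the data are seen would be post hoc.

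**Working it through.** **1. The plan's own figure, and what it covers.** Section 11.1 gives 76 per arm, with 80% power for 10% versus 30% and 90% power for 10% versus 33%. Sidedness is not stated, so two-sided 0.05 is assumed.

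n = [1.96·√(2p̄q̄) + z·√(p₁q₁ + p₂q₂)]² / d²

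For 10% versus 30%: [1.96·√0.32 + 0.8416·√0.30]² / 0.04 = 61.6, so 62 per arm. For 10% versus 33% at 90% power the result is 65. With a continuity correction these become 72 and 74. Dividing by 0.95 for an assumed 5% dropout (not in the documents) gives 76 and 78. The stated size is therefore reproduced. It applies to one comparison of remission proportions, and the primary comparison is at week 24.

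**2. What four separate proportions say about persistence.** Let p be the proportion in remission at each of the four visits. With no rule linking the visits, the proportion in remission at all four lies between max(0, 4p − 3) and p. The values of p below are assumptions.

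| Assumed p at each visit | Lower bound | Upper bound | Of 76 |
|---|---|---|---|
| 10% | max(0, 0.40 − 3) = 0 | 10% | 0 to about 8 |
| 20% | max(0, 0.80 − 3) = 0 | 20% | 0 to about 15 |
| 30% | max(0, 1.20 − 3) = 0 | 30% | 0 to about 23 |
| 40% | max(0, 1.60 − 3) = 0 | 40% | 0 to about 30 |

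With declining proportions of 30%, 25%, 20% and 15%, the upper bound is the smallest, 15%, or about 11 of 76. The lower bound is again 0. These ranges hold only if the visits are unconstrained, which is why the censoring sentence matters.

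**3. Reading A: censored means not in remission at all later visits.** If this applies after any visit without remission, the week-64 proportion equals the proportion in remission at all four visits, and the range in step 2 disappears. If it applies only after a Section 5.3.3 relapse, one route stays open. A drug-free sequence of 6.3%, 6.7%, 6.3% loses and regains remission without reaching 7.0%. Whether failing to achieve remission covers the middle visit is unclear, because that phrase names no visit.

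**4. Reading B: censored means removed from the denominator.** Suppose week 24 shows 30% versus 10%, that is 0.30 × 76 = 22.8 (about 23) and 0.10 × 76 = 7.6 (about 8). If those who failed at week 24 are then removed, 76 − 23 = 53 and 76 − 8 = 68 participants leave, and week 36 compares 23 people with 8. If all of these stay in remission, the result is 23/23 versus 8/8, a difference of 0. With everyone kept, it is 23/76 − 8/76 = 30.3% − 10.5%, about 20 points. Reading B thus compares groups selected by their own outcome, and it contradicts the inclusion of all participants earlier in Section 11.2.

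**5. Reading C: censored in the time-to-event sense.** No such analysis is planned. If one were, relapse would be the event and not a reason for censoring.

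**The case against.** The strongest reply is that the censoring sentence already prevents people from drifting in and out of remission. A participant with HbA1C of 7.0% or more, or who restarts a drug, has relapsed under Section 5.3.3 and is censored. A participant who never remitted is named in the same sentence. Under Reading A or B, none of these is counted later as a new remission. This stands. A reader might infer that relapsed participants can freely regain remission in the counts, or that the 0-to-23 range describes the plan as written. The documents support neither. The only route clearly outside the relapse rule is the 6.5-6.9% band.

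A reader might also infer that the trial cannot show whether anyone stayed in remission. That is too strong. HbA1C and drug use are recorded on the same people at weeks 24, 36, 48 and 64, so persistence can be derived; it is just not prespecified. Nor is remission purely a single-visit status, since it requires 12 weeks off drugs. That condition governs time off drugs, however, and not how long HbA1C has been below 6.5%.

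It is fair to add that the primary question, objective and analysis agree on week 24, and that later outcomes are only hypothesis-generating. Section 5.3.3 also answers its own warning about HbA1C lag by adding the drug and home-glucose criteria. The primary test is therefore sound for what it tests. What is left is a hypothesis without a matching outcome and a counting rule that must be guessed.

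**Conclusion.** The concern holds in a limited form. Sustained remission is hypothesised but neither defined nor estimated, and the censoring sentence does not settle the matter. Under one reading the week-64 proportion is close to sustained remission, with the 6.5-6.9% band unresolved. Under another it conflicts with intention-to-treat, and in the illustration it turns a difference of about 20 points into 0. Those figures assume 30% versus 10% at week 24, removal of all who failed then, and no later relapse. The range of 0 to about 23 of 76 assumes 30% at each visit and no link between visits. It shows what separate proportions leave open and does not predict the trial's result.

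A reader might infer that the primary outcome should itself become sustained remission. The documents do not require this, and the sample size was not set for it. If 75%, 50% or 25% of week-24 remitters in both arms stayed in remission (assumed), the rates would be 22.5% versus 7.5%, 15% versus 5%, or 7.5% versus 2.5%. Power at 76 per arm would be about 74%, 54% or 29%, against 88% for 30% versus 10%, all without continuity correction.

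**What to change.** 1. In Sections 6.2.1 and 11.2, add a secondary outcome of sustained remission: remission at week 24 and at every later scheduled visit to week 64, with no glucose-lowering drug and no Section 5.3.3 relapse in between. Report it also to weeks 36 and 48. Keep all randomized participants in the denominator, carry over the existing dropout rule, and use the same chi-squared test and risk difference with 95% confidence interval.
2. Replace the censoring sentence in Section 11.2 with a statement that a participant who relapses counts as not in remission at later visits and stays in the denominator.
3. State how a drug-free visit at 6.5-6.9% after remission is handled in the visit-wise outcomes. In the sustained outcome such a visit ends remission by definition.
4. Leave the primary outcome and sample size unchanged, and limit the primary conclusion to remission at week 24.

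This changes how outcomes are counted and does not affect how relapse is managed. It costs one derived variable and one table from data already collected. The downside is that the sustained proportion cannot exceed any of the visit-wise ones, so the estimate may be small and imprecise. It should be settled before outcome data are seen.

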#### **Primary research question:**

In patients with recently-diagnosed T2DM, does a 12-week course of Forxiga, metformin, basal insulin glargine and lifestyle approaches achieve drug-free diabetes remission in a higher proportion of patients than standard diabetes therapy at 24 weeks after randomization? Diabetes remission is defined as a HbA1C < 6.5% off glucose-lowering agents for at least 12 weeks.

**Secondary research questions:**

- 1) Compared to the control group, does this therapeutic approach achieve drug-free diabetes remission in a higher proportion of patients than standard diabetes therapy at 36, 48 and 64 weeks after randomization?
- 2) Compared to the control group, does this therapeutic approach achieve drug-free HbA1C <6.0% in a higher proportion of patients than standard diabetes therapy at 24, 36, 48 and 64 weeks after randomization?
- 3) Compared to the control group, does this therapeutic approach achieve drug-free diabetes regression in a higher proportion of patients than standard diabetes therapy at 24, 36, 48 and 64 weeks after randomization? Diabetes regression is defined as HbA1C 6.5-6.9% off glucose-lowering agents for at least 12 weeks.
- 4) What HbA1C levels are achieved in the intervention group and the control group at 12, 24, 36, 48 and 64 weeks after randomization?
- 5) What rates of hypoglycemia are observed in the intervention group and the control group during 64 weeks of follow-up?
- 6) What is the change in weight, body mass index (BMI), waist circumference and waist/hip ratio from baseline to 12, 24, 36, 48 and 64 weeks in the intervention group and the control group?
- 7) Are age, gender, ethnicity, diabetes duration, smoking, family history of diabetes, baseline BMI, waist circumference, HbA1C or fasting plasma glucose (FPG) determinants of diabetes remission at 24 weeks after randomization?

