**2.2 Secondary objectives**

To determine whether the 12-week metabolic intervention that includes Forxiga is more effective than standard diabetes therapy in achieving diabetes remission and regression when evaluated at 36, 48 and 64 weeks after randomization.

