## **11. STATISTICAL METHODS AND SAMPLE SIZE DETERMINATION**

### **11.1 Proposed sample size and justification**

The sample size calculation is based on the estimated proportion of patients achieving diabetes remission of 10% in the control group. The control group estimate of 10% is based on the proportion of patients in the conventional diabetes treatment group of 13% who achieved FPG < 7.0 mmol/L and HbA1C < 6.2% off therapy after 2 years of follow-up observed in the Dixon *et al.* trial, after adjusting for the longer duration of diabetes since diagnosis in participants in our trial ( $\leq 8$  years versus < 2 years). A total sample size of 152 participants (76 per treatment group) will provide 80% power to show a risk difference of  $\geq 20\%$  in the induction of diabetes remission between treatment groups and 90% power to show a risk difference of  $\geq 23\%$ .

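### Secondary question 3 tests a closed drug-free HbA1C band that excludes remission, so its between-group difference cannot be read alone as benefit or harm

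*Combined protocol and SAP*

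**What the plan says.** Section 1.2 defines remission as drug-free HbA1C below 6.5%. Secondary question 3 then asks whether the intervention will "achieve drug-free diabetes regression in a higher proportion of patients than standard diabetes therapy" at 24, 36, 48 and 64 weeks, with this definition: "Diabetes regression is defined as HbA1C 6.5-6.9% off glucose-lowering agents for at least 12 weeks". Section 6.2.1 repeats it as "diabetes regression, defined as a HbA1C of 6.5-6.9% without use of glucose-lowering agents for at least 12 weeks". Section 2.2 makes it a superiority objective: to show that the intervention is "more effective than standard diabetes therapy in achieving diabetes remission and regression when evaluated at 36, 48 and 64 weeks after randomization".

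The neighbouring outcomes are built differently. The primary outcome has a single upper cut-off, and so does question 2: "achieve drug-free HbA1C <6.0% in a higher proportion of patients than standard diabetes therapy".

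Section 11.2 compares groups by intention to treat with all participants included, assigns a chi-squared test to dichotomous secondary outcomes, and limits secondary outcomes to generating hypotheses. Its rule for withdrawals is written for remission only. No section defines a combined drug-free outcome below 7.0%, although section 5.3.3 draws the HbA1C line for relapse at or above "7.0% at 24, 36, 48 and 64 weeks".

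**The concern.** With a single cut-off, a higher proportion always means that more participants reached that level or better. The regression band has two edges, and participants cross both. Crossing the upper edge downwards (relapse to regression) adds to the count. Crossing the lower edge downwards (regression to remission) takes away from it. The second move is the one the trial most wants to produce, and question 3 scores it as a failure.

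A small or non-significant difference could then be reported as no effect on regression while more participants are drug-free below 7.0%. A lower proportion could be reported as an unfavourable finding when it reflects more remission. Section 2.2 invites such statements by asking for superiority on regression.

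**Working it through.** **1. The plan's own figure.** Section 11.1 states: "A total sample size of 152 participants (76 per treatment group) will provide 80% power to show a risk difference of" at least 20 points, from a 10% control rate, and 90% power for 23 points. With the usual two-proportion formula, two-sided alpha 0.05 (the plan does not state sidedness) and 76 per arm:

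- 10% vs 30%: power 87.7% without and 82.9% with continuity correction.
- 10% vs 33%: power 94.0% without and 91.1% with continuity correction.

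The stated power is met. These figures concern remission only.

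**2. An identity that needs no model.** Remission and regression do not overlap, and together they make up drug-free HbA1C below 7.0%. Writing D for intervention minus control:

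D(band) = D(below 7.0%) - D(below 6.5%)

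At the planned remission gain of 20 points, the band difference is positive only if the gain below 7.0% exceeds 20 points. A gain of 15 points below 7.0% would give 15 - 20 = -5 points on regression, with the intervention better on both single cut-offs.

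**3. What the documents leave open.** They give remission rates for planning. They give no HbA1C SD, no share of each arm that is drug-free, no regression rate, and no planning rates specific to 36, 48 or 64 weeks. The rest is therefore an assumed model: HbA1C among drug-free participants is normal with SD s, a share f of each arm is drug-free, and the band is 0.5 wide (6.5 to 7.0). For remission rate p:

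- mean = 6.5 - s × z(p/f), where z is the standard normal quantile
- P(below 7.0%) = f × Φ((7.0 - mean)/s)
- band rate = P(below 7.0%) - p

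Example: p = 10%, f = 1, s = 1.0. Mean = 6.5 + 1.282 = 7.782; Φ(-0.782) = 21.7%; band = 21.7 - 10 = 11.7%. For p = 30%: mean = 7.024; Φ(-0.024) = 49.0%; band = 19.0%. Difference +7.3 points.

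**4. Results at 10% vs 30% remission, 76 per arm, same SD in both arms.** Rates are control vs intervention; differences are in percentage points.

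| Drug-free share, each arm | SD | Band | Band difference | Difference below 7.0% |
|---|---|---|---|---|
| 100% | 0.6 | 22.7 vs 32.1% | +9.4 | +29.4 |
| 100% | 0.8 | 15.6 vs 24.0% | +8.4 | +28.4 |
| 100% | 1.0 | 11.7 vs 19.0% | +7.3 | +27.3 |
| 100% | 1.2 | 9.4 vs 15.7% | +6.4 | +26.4 |
| 50% | 0.6 | 14.8 vs 13.1% | -1.8 | +18.2 |
| 50% | 1.2 | 6.8 vs 7.4% | +0.7 | +20.7 |
| 40% | 0.6 | 12.5 vs 7.4% | -5.2 | +14.8 |
| 40% | 1.2 | 5.9 vs 4.5% | -1.4 | +18.6 |

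Differences were taken before rounding. With everyone drug-free, power for the band difference is 22-26%, and power for the difference below 7.0% is 94-96%.

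**5. Unequal spread.** With everyone drug-free and control SD 0.6, an intervention SD of 1.0 gives 22.7 vs 19.0% (-3.7 points), and an SD of 1.2 gives 22.7 vs 15.7% (-7.0 points). The differences below 7.0% are then +16.3 and +13.0 points.

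Remission improves by 20 points in every row. The band difference changes sign; the difference below 7.0% does not.

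**The case against.** The strongest reply is that nothing in the plan requires regression to be read alone. Remission is compared at the same visits (24 weeks as primary; 36, 48 and 64 weeks in question 1), drug-free HbA1C below 6.0% and HbA1C levels are reported beside it, and section 6.2.1 presents regression as an outcome related to remission. The categories share visits and denominators, so a reader can add them. Section 11.2 treats all secondary results as hypothesis-generating. The combined outcome also largely repeats the primary: with everyone drug-free, 20 of its 26.4 to 29.4 points (68-76%) are remission itself, which already has 88% power by the uncorrected formula.

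Most of this stands, and it keeps the severity low. It does not remove the defect, because question 3 and section 2.2 still ask for a higher regression proportion and section 11.2 still tests it. A sum formed after the results are known is not prespecified.

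Two stronger readings are tempting, and the documents support neither.

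- A reader might infer that the regression difference will be reversed in a successful trial, pointing to pilot results that "induced remission in up to 40% of people with early T2DM", or conversely that it will be small and positive. The planning rates fix only the proportion below 6.5%. The sign depends on the SD and the drug-free share, which are not given.
- A reader might infer that the censoring sentence in section 11.2 removes participants in the 6.5-6.9% band from question 3. That sentence is confined to remission outcomes and does not mention regression, so the loss is not shown. Its meaning for remission is a separate matter.

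**Conclusion.** The concern holds as a problem of interpretation. Regression as defined does not rise steadily with benefit, so a higher, equal or lower proportion cannot by itself be called benefit or harm. This follows from the definitions and needs no model.

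The size and direction of the difference are undetermined from the documents. Under the assumed normal model at 10% vs 30% remission, it is about +6 to +9 points if all are drug-free with SD 0.6-1.2, about -5 to -1 points if 40% of each arm is drug-free, and negative when the intervention SD is clearly larger than the control SD. Even in the favourable case, power is only 22-26%, so a non-significant result would be likely when the intervention works as planned. The 24-week planning rates should not be carried to later visits: return to standard care after relapse can lower the drug-free share.

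The change is worth making but optional. The primary outcome is unaffected and secondary outcomes are hypothesis-generating.

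**What to change.** Prespecify, as the between-group comparison for question 3, the proportion with drug-free HbA1C below 7.0% (remission or regression, with no glucose-lowering drug for 12 weeks or more) at 24, 36, 48 and 64 weeks. This agrees with the HbA1C relapse line in section 5.3.3. Report the 6.5-6.9% band as n (%) per arm beside remission, without reading its difference alone as an effect.

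Suggested text for section 11.2: *For drug-free HbA1C below 7.0%, all randomized participants stay in the denominator and are classified by the definition at each visit. Anyone who withdraws before a visit is classified as not having achieved the outcome at that visit. The outcome contains remission and is not independent evidence of effect.*

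Align sections 1.2, 2.2, 6.2.1 and 11.2.

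The cost is the wording of one secondary outcome and a few sentences in section 11.2, with the same visits and data. The small downside is that the new result is correlated with remission, which the suggested text discloses.
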